6.2. Ordering

The drug will be supplied by Oncovir and shipped to the UAB Investigational Drug Service (IDS), which is designated as the Central Pharmacy. The UAB IDS is responsible for the transfer and transportation of shipment of poly-ICLC to study sites. Transport of poly-ICLC to study sites must be pre-approved by the sponsor and IRB before any study drug will be transported. Poly-ICLC will be transported in accordance with specific storage requirements.

When study drug is needed at a study site, an electronic ordering system is utilized for planned transport of study drug, with date and time specifications included in the request. To initiate an order, the UAB IDS ordering form will be sent to [contact]. Once received, NFCTC will approve the order and forward to UAB IDS. UAB IDS will arrange the transportation to the requesting site. Poly-ICLC will be shipped out 3-7 business days after the UAB IDS ordering form is received. Once the study site receives the shipped product, the form must be completed and sent back to [contact].

Drug Distribution Center - UAB Research Pharmacy

- According to 21 CFR 312.6, UAB IDS will label the packaging of the investigational drug with the following statement: "Caution: New Drug - Limited by Federal law to investigational use".
- UAB IDS will maintain records showing the receipt, shipment, and other pertinent information of the investigational drug including:
 - Name of the investigator to whom the drug is shipped
 - Date, quantity, and batch number of each shipment
 - Return, destruction, or other appropriate disposition of unused study drug

UAB Research Pharmacy

Attention: [name], PhD, MBA | Pharmacy Manager/IDS Pharmacy
North Pavilion | Room 3470 | [name] | Birmingham, AL, 35249
[contact] or [contact] | [contact]

6.3. Drug Accountability

The research pharmacist at each participating site will maintain records of all dispensed vials of study drugs. All unused vials will be returned to the manufacturer (Oncovir) at the completion of the study as well as all the drug accountability forms.

6.4. Dose Modifications for Toxicity

Dose modifications below apply to toxicities that are at least possibly related to study drug. Laboratory results requiring drug hold must be repeated weekly or sooner if clinically indicated until they meet the criteria for restarting drug.

Liver Toxicity

If AST/ALT > 5x ULN while on study, poly-ICLC will be held until the AST/ALT \leq 5x ULN; if resolved within 21 days, maintain the dose 20 mcg/kg/dose twice weekly.

If event resolves >22-28 days, hold study drug until values < 2.5x ULN then restart at the reduced dose of 10 mcg/kg/dose twice weekly.

If AST/ALT do not decrease to \leq 5x ULN within 28 days (despite holding the drug for 28 days and only if elevated AST/ALT is attributable to the drug), then the study drug will be stopped, and participant will be off treatment for toxicity.

It is recommended to evaluate other medications that participant is taking for potential liver toxicity (e.g. acetaminophen, trimethoprim/sulfamethoxazole, seizure medications). It is also recommended to evaluate potential viral liver infection if there is persistent elevation of AST/ALT.

Elevations of AST/ALT are expected, and repeat elevations do not require permanent drug discontinuation unless deemed medically necessary by the treating physician after discussion with the principal investigator.

Hematological Toxicities: Thrombocytopenia

Continue drug at 20 mcg/kg/dose unless platelet count is less than 75,000/mm³. Then refer to the table below for further instructions.

Platelet (Plt) < 75,000/mm ³	Interrupt study drug until Plt \geq 75,000/mm ³ . If the event resolves within 21 days, then study drug may be restarted at the same dose. If Plt count of <75,000/mm ³ attributable to the study drug, and the event resolves between 22-28 days, then study drug may be restarted at lower dose of 10 mcg/kg/dose. If Plt is <75,000/mm ³ after 28 days and at least "possibly" attributed to study drug, the participant will be taken off protocol therapy. Transient and repeated thrombocytopenia is expected and does not require permanent removal from study therapy unless deemed medically necessary by the treating physician after discussion with the principal investigator or study team.
---	---

Hematological Toxicities: Neutropenia

Continue drug same dose until absolute neutrophil count (ANC) is less than 750/mm³, then refer to the table below for further instructions.

ANC < 750/mm ³	
Interrupt study drug until resolution to ≥ 750/mm³. If the event resolves within 21 days, then study drug may be restarted at the same dose. If event resolves between days 22 and 28, restart at lower dose of 10 mcg/kg/dose.
 
If ANC is < 750/mm³ greater than 28 days after dose reduction, and at least “possibly” attributed to the study drug, the participant will be taken off protocol therapy.
 
Transient and repeated neutropenia is not unexpected and does not require permanent removal from study therapy unless deemed medically necessary by the treating physician after discussion with the principal investigator or study team.

---------------------------	---

All other adverse events (suspected to be related to the study drug)	
Grade 1-2	
Grade 1 AE continue drug same dose 20 mcg/kg/dose. Provide specific therapy to address symptoms.
 
If the event is an intolerable Grade 2 AE, not responsive to a specific therapy, consider study drug interruption until resolution to Grade ≤1. If the event is clinically significant and resolves within 21 days, then study drug may be restarted at same dose. If event resolves between days 22 and 28, restart at a lower dose of 10 mcg/kg/dose. If the patient continues to have grade 2 intolerable toxicity despite dose reduction and providing specific therapy to address symptoms, protocol therapy will be permanently discontinued.

Grade 3 and Grade 4	
Interrupt study drug until resolution to Grade ≤1. If the event resolves within 21 days, then study drug may be restarted at the same dose. If event resolves between days 22 and 28, or the patient has a repeat grade 3 or grade 4 event, restart at lower dose of 10 mcg/kg/dose. If toxicity returns

	to grade 3 or 4 after drug reduction, protocol therapy will be permanently discontinued.
--	--

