5.2. Evaluation During Treatment (See Appendix 3)

- A. Disease evaluation with MRI brain (with orbital cuts for optic pathway tumors) or spine MRI depending on the primary tumor site every 3 cycles (+/-2 weeks) while on therapy (to be done at the end of the cycle). CSF cytology if clinically indicated. Tumor Evaluation forms are to be completed every 3 cycles while participant is on study. More frequent MRIs can be done at the treating physician discretion. Every MRI performed on participants on study will be submitted to the NFCTC Operations Center for central review at the conclusion of the study.
- B. History, vital signs, physical and neurological examination and concomitant medication list, on cycle 1 day 1 and cycle 1 day 15 (+/-48 hours) and on day 1 (+/-5 days) of each subsequent cycle.
- C. Labs:
 - (a) CBC/differential, platelets are to be obtained on cycle 1 day 1 if not performed within 14 days, on cycle 1 day 8 (+/-48 hours) and cycle 1 day 15 (+/-48 hours) and on day 1 (+/-5 days) of each subsequent cycle.
 - (b) CMP (including sodium, potassium, CO₂, chloride, total protein, glucose, AST, ALT, alkaline phosphatase, albumin, calcium, total bilirubin, BUN, creatinine, phosphorous) are to be obtained on cycle 1 day 1 if not performed within 14 days and on day 1 (+/-5 days) of each subsequent cycle.

Biological correlates SHOULD NOT be obtained on a Friday.

- D. Pregnancy test if female patient is of childbearing age.
- E. Toxicity monitoring and review of medication diary and temperature log at every visit after starting study treatment.
- F. Lansky Play Scale assessment for participants < 16 years of age; Karnofsky score for participants \geq 16 years old at baseline, cycle 1 day 15, and then prior to each cycle (see Appendix 3).
- G. Ophthalmology Functional Assessments (see section 9) only for patients with optic pathway gliomas at the end of cycle 3 (+/- 2 weeks) then every 3 cycles (+/-2 weeks) until end of treatment.
- H. QOL Assessment will be done on day 1 Cycle 6 (+/-2 weeks) and day 1 cycle 12 (+/- 2 weeks) and end of cycle 24 or end of therapy (+/- 2 weeks) (see section 8).

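### In cycle 1 the AST/ALT hold has no scheduled post-dose result until cycle 2 day 1; adding AST/ALT to the existing day 8 and day 15 draws is a cheap improvement, not the repair of a design defect

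*Combined protocol and SAP*

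**What the plan says.** Section 6.4 sets the liver rule: "If AST/ALT > 5x ULN while on study, poly-ICLC will be held until the AST/ALT" returns to 5x ULN or less. The rule is limited by attribution: "Dose modifications below apply to toxicities that are at least possibly related to study drug". For an elevation that clears quickly, "if resolved within 21 days, maintain the dose 20 mcg/kg/dose twice weekly". The section also says: "Elevations of AST/ALT are expected, and repeat elevations do not require permanent drug discontinuation".

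AST and ALT are part of the CMP. Section 5.2 C(b) has it "obtained on cycle 1 day 1 if not performed within 14 days and on day 1 (+/-5 days) of each subsequent cycle". The Appendix 3 CMP row and footnote 6 agree. So does the Appendix 9 roadmap, where the CMP (observation C) appears on day 1 only; day 8 lists B and D, and day 15 lists A, B, D and E.

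The CBC, which serves the platelet and ANC holds in the same section 6.4, is also drawn "on cycle 1 day 8 (+/-48 hours) and cycle 1 day 15 (+/-48 hours"). Section 5.2 I puts research blood on the same two days and bars a fingerstick.

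**The concern.** Section 6.4 names three laboratory holds: liver, platelets and neutrophils. In cycle 1 the last two have scheduled results on days 8 and 15. The liver hold has none after dosing starts until C2D1. Doses after the first may be given at home, and no visit is scheduled between C1D15 and C2D1.

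The repeat-testing rule does not fill the gap: "Laboratory results requiring drug hold must be repeated weekly or sooner if clinically indicated until they meet the criteria for restarting drug". It starts only once a result has already required a hold.

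Three features make an early value useful:
- Section 3.1 allows entry with AST/ALT up to 5x ULN, the hold limit itself, although inclusion 8 also requires recovery to grade 1 or less from acute toxicity of prior treatment.
- Section 6.4 advises, when AST/ALT is raised: "It is recommended to evaluate other medications that participant is taking for potential liver toxicity (e.g. acetaminophen" is the first example given. Appendix 9 recommends acetaminophen or ibuprofen around each injection.
- The dose after a hold depends on how long resolution takes (up to 21 days, 22-28 days, or longer), which is hard to judge when onset was not seen.

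At stake is a modest amount of patient safety: whether an asymptomatic elevation above the limit is seen while doses can still be held. The primary endpoint is not involved.

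**Working it through.** The plan states no figure for this interval, so there is none to reproduce. The check is a count of days and doses.

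**Inputs**
- Dose days: 1, 4, 8, 11, 15, 18, 22, 25 (Appendix 9). With a Thursday or Friday start they become 1, 5, 8, 12, 15, 19, 22, 26.
- No dose after the eighth until the clinic visit (Appendix 8).
- C2D1 = day 29 +/- 5 = days 24-34. C1D8 +/- 48 h = days 6-10. C1D15 +/- 48 h = days 13-17 (section 5.2).
- Assumption: the +/- 5 days is applied once to C2D1. This agrees with the 33-day supply limit in section 4.2.

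**Present plan**
- First scheduled post-dose AST/ALT: 29 - 1 = 28 days after the first dose; range 24 - 1 = 23 to 34 - 1 = 33.
- Doses given before it: 7 if drawn on day 24; 8 if drawn on day 29 or day 34 (capped at 8).
- Time on drug without a value: 25 - 1 = 24 days; 26 - 1 = 25 with a Thursday or Friday start; 24 - 1 = 23 if C2D1 falls on day 24.
- The baseline CMP may be 14 days old, so two consecutive scheduled values can lie 14 + 28 = 42 days apart, at most 14 + 33 = 47.

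**CBC, for comparison**
- First post-dose value: 8 - 1 = 7 days; range 6 - 1 = 5 to 10 - 1 = 9; after 2-3 doses.

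**With AST/ALT on days 8 and 15**
- First value at 7 days (5-9), after 2-3 doses, so 8 - 3 = 5 to 8 - 2 = 6 doses follow a scheduled draw.
- Second value at 14 days (12-16), after 4-5 doses.
- Longest on-drug stretch without a value = max(D8 - 1, D15 - D8, last dose day or C2D1 if earlier - D15). Nominal: max(7, 7, 25 - 15) = 10, or max(7, 7, 26 - 15) = 11. Over all visit windows: 8 (for example draws on days 9 and 17, C2D1 on day 24: max(8, 8, 7)) to 13 (26 - 13).

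**Children under 10 kg, day 15 only**
- First value at 14 days (12-16), after 4-5 doses. Longest on-drug stretch: nominal max(15 - 1, 25 - 15) = 14, range 12-16.

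**Recording delay**
- A hypothetical elevation present on C1D8 and lasting to C2D1 is first recorded 29 - 8 = 21 days later (24 - 10 = 14 to 34 - 6 = 28). This is calendar arithmetic, not an expected loss.

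**Later cycles**
- In cycles 2-24 both CBC and CMP are drawn on day 1 only, so the contrast between the holds exists only in cycle 1.

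**The case against.** The strongest reply is that this is a monitoring preference. The schedules agree with one another, section 6.4 promises no within-cycle chemistry, and from cycle 2 all three laboratory holds rest on day 1 draws. That stands: nothing in the plan is contradicted or breached.

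There is also visible support for watching blood counts more closely. Section 6.5 cites intratumoral hemorrhage risk with thrombocytopenia, and section 2.3 reports grade 3 leukopenia in a child with LGG on poly-ICLC. Sections 6.1 and 6.6 describe liver-enzyme rises with intravenous dosing as transient and, in 6.6, mild. Section 2.3 reports little or no toxicity in adults on long-term intramuscular 10-50 mcg/kg. This lowers the likely benefit but does not remove it, because section 6.4 itself calls elevations expected and makes the hold mandatory.

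Existing safeguards limit the harm. Section 4.2.1 blocks cycle 2 if AST/ALT exceeds 5x ULN, toxicity is evaluated on days 8 and 15, and unscheduled tests are not barred. An elevation that resolves within 21 days leads only to a restart at the same dose. None of these would reliably show an asymptomatic rise during cycle 1 dosing.

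A reader might infer that the hold cannot operate in cycle 1, or that participants are left unprotected. The documents do not support that: an unscheduled result can trigger the hold, and C2D1 catches what persists. A reader might also infer that the toxicity endpoint in section 14 is compromised. Sections 11.1 and 11.4 keep non-clinically significant laboratory values out of adverse event recording, so any gain in grade and duration is confined to clinically significant elevations.

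**Conclusion.** The gap exists and is consistent across section 5.2, Appendix 3 and Appendix 9: in cycle 1 the liver hold has no scheduled post-dose result for 28 days (23-33), by which time 7-8 of 8 doses have been given. Closing it is a recommended change at the optional end: a modest safety gain at low cost. It does not show an error in the design.

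The day counts rest on the Appendix 9 dose days, the eight-dose cap in the diary and a single +/- 5-day window at C2D1. The benefit rests on elevations above 5x ULN arising before about day 25 with intramuscular dosing. The documents available give no rate or timing for these, and the text of section 2.4, on the earlier pediatric trial, was not available. The number of events that would be caught is therefore unknown, and the lack of a rate is not held against the plan.

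**What to change.** Add AST/ALT to the existing C1D8 and C1D15 draws in section 5.2 C(b), the Appendix 3 CMP row and footnote 6, and the day 8 and day 15 rows of Appendix 9. For patients under 10 kg, test on C1D15 only, because their research collection on C1D8 is set at 2 ml. Leave the hold threshold, dose and visit schedule as they are.

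Cost:
- At most 2 x 20 = 40 scheduled added tests, all in cycle 1, with no added scheduled visit or needle stick, since research blood is already drawn on both days and not by fingerstick.
- Weekly repeats under section 6.4 for any participant whose result requires a hold. A hold on day 15 could need an unscheduled visit near day 22.
- Slightly more blood, which matters most in the smallest children.
- Some temporary holds for elevations that would have resolved unnoticed.

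A narrower option is to test only participants with AST/ALT above ULN at baseline. It costs less but misses new elevations in those who start normal.

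### The short-hold liver rule in section 6.4 names 20 mcg/kg as the restart dose, which is ambiguous for a participant already reduced to 10 mcg/kg

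*Combined protocol and SAP*

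**What the plan says.** Section 6.4 (Dose Modifications for Toxicity) opens by limiting its scope: "Dose modifications below apply to toxicities that are at least possibly related to study drug". The liver rule holds drug when AST/ALT exceeds 5 times the upper limit of normal (ULN) until values are back at or below that level, and then gives the short-hold instruction: "if resolved within 21 days, maintain the dose 20 mcg/kg/dose twice weekly". If resolution takes 22 to 28 days, the instruction is to "hold study drug until values < 2.5x ULN then restart at the reduced dose of 10 mcg/kg/dose twice weekly". The section adds: "Elevations of AST/ALT are expected, and repeat elevations do not require permanent drug discontinuation", unless the treating physician, after discussion with the principal investigator, judges discontinuation necessary.

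The other short-hold rules name no dose. The thrombocytopenia rule is typical: "If the event resolves within 21 days, then study drug may be restarted at the same dose". The neutropenia and Grade 3-4 rules use the same sentence, and the Grade 2 rule has the same effect.

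A fixed 20 mcg/kg also appears in three places that are not restart rules: the thrombocytopenia lead-in ("Continue drug at 20 mcg/kg/dose unless platelet count is less than" the 75,000/mm³ threshold), the Grade 1 row ("Grade 1 AE continue drug same dose 20 mcg/kg/dose"), and the dose column of the roadmap for cycles 2-24 in Appendix 10.

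**The concern.** A restart rule has to work for every participant who can reach it, at whichever dose that participant is receiving. The liver rule combines a verb meaning no change with a number that is a change for anyone on the reduced dose, and both cannot be followed at 10 mcg/kg.

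The case that matters most is a child reduced to 10 because an earlier liver event took 22 to 28 days to resolve, and who had to wait for values below 2.5 times ULN before restarting. If that child later has a short elevation, the printed number returns the child to the dose that was reduced, at up to 5 times ULN. Injections may be given at home (section 4.2), and once restart criteria are met the next routine chemistry is on day 1 of the following cycle (section 5.2), so a misreading could last until then. In a multi-center trial, two sites could also treat the same event differently.

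**Working it through.** There is no statistical figure to reproduce. The check compares the rules in section 6.4, asks whether a reduced participant can reach the liver rule, and looks for any other text that settles the dose.

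**Step 1. The five rules for a hold resolving within 21 days.**

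| Rule in section 6.4 | Restart dose stated | Participant on 20 | Participant on 10 |
|---|---|---|---|
| Liver (AST/ALT > 5 × ULN) | 20 mcg/kg, with the verb maintain | 20 | 10 or 20 |
| Platelets < 75,000/mm³ | unchanged | 20 | 10 |
| ANC < 750/mm³ | unchanged | 20 | 10 |
| Intolerable Grade 2 | unchanged | 20 | 10, unless the stop clause applies |
| Grade 3-4 | unchanged | 20 | 10, unless the stop clause applies |

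Four of the five name no number; one does. The stop clauses are taken up under the objection.

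**Step 2. Can a participant be on 10 mcg/kg?** Yes, by six routes in section 6.4:

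1. a liver event resolving on days 22-28, with restart once values are below 2.5 × ULN;
2. low platelets resolving on days 22-28;
3. a low ANC resolving on days 22-28 ("If event resolves between days 22 and 28, restart at lower dose of 10 mcg/kg/dose");
4. an intolerable Grade 2 event resolving on days 22-28;
5. a Grade 3-4 event resolving on days 22-28;
6. a repeat Grade 3-4 event.

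Five of the six are non-hepatic. After any of them, a first AST/ALT elevation that clears within 21 days brings the participant to the liver rule. After the hepatic route, a repeat elevation does so, because repeats do not require stopping. Treatment can run for 24 cycles.

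**Step 3. Does other text settle the dose?**

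- Section 3.5(d) removes a participant who has gone more than 28 days without drug. It does not address shorter holds.
- Section 4.2.1 gives AST/ALT thresholds for starting a cycle, but no dose.
- Appendix 10 prints only 20 mcg/kg. Its blank mcg entry for each injection allows an individual dose but does not say which one is right.
- Nothing in the text reviewed permits or bars re-escalation after a reduction.

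**Step 4. Size of the difference between the two readings.**

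- Per week: 2 injections × 10 = 20 mcg/kg, against 2 × 20 = 40 mcg/kg.
- Per 28-day cycle: 8 injections × 10 = 80 mcg/kg, against 8 × 20 = 160 mcg/kg.
- Ratio: 160 / 80 = 2.

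**The case against.** The strongest reply is that the sentence already answers the question. To maintain a dose is to leave it alone, and the 20 describes the participant the author had in mind, one not yet reduced. The liver sentences then read as a pair: stay at the starting dose after a short hold, go down after a longer one. The Grade 1 row uses 20 in the same way, as a gloss on an unchanged dose. Every explicit dose change in section 6.4 is downward, so reading the rule as an order to double a reduced dose after hepatotoxicity is strained. This stands as an account of likely intent. It does not remove the printed number, which is the only dose the rule gives.

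A second reply is that the contrast with the other rules is less clean than a four-to-one count suggests. The Grade 2 and Grade 3-4 rows end protocol therapy if the toxicity persists or returns after reduction, so for a recurrence of the same toxicity the unchanged-dose wording is overridden. That is correct, and it leaves platelets and ANC as the cleanest comparators. But those stop clauses belong to the table for all other adverse events and do not govern the liver rule.

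A third reply is that little is at stake. Two successive events are needed in a trial of at most 20 participants. The worse outcome is the protocol's standard dose, inside the 10 to 50 mcg/kg low-dose range in section 2.2 and far below the maximal tolerated dose of 250-300 mcg/kg in section 6.1. The roadmap has a physician signature line, and laboratory values requiring a hold are repeated at least weekly until restart criteria are met. All of this is fair and supports a minor rating. None of these safeguards states the restart dose.

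**Conclusion.** The concern holds, as a minor point. The plan does not order re-escalation. It gives a dosing instruction that supports two readings for a participant on 10 mcg/kg, and the readings differ by a factor of 2. The wording looks like a drafting inconsistency rather than a deliberate choice.

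The conclusion rests on the text of section 6.4 and on finding no clarifying rule elsewhere in the text reviewed. That text gives no frequency for a reduction followed by a short liver hold, so the number of participants affected cannot be estimated beyond the ceiling of 20 enrolled; section 2.4, on the earlier pediatric trial, was not available. The primary endpoint definition, the sample size of 16 evaluable participants and the test are unaffected. The fixed 20 in the thrombocytopenia lead-in, the Grade 1 row and Appendix 10 is a matter of consistency only, and the conclusion does not depend on it.

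**What to change.** Change the short-hold liver instruction in section 6.4 to: *if resolved within 21 days, restart at the dose the participant was receiving before the hold (20 or 10 mcg/kg, twice weekly)*. This brings it into line with the other short-hold rules and changes nothing for a participant on 20.

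Three tidy-ups can go in the same amendment:

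- In the thrombocytopenia lead-in, replace the fixed dose with *the current dose*.
- In the Grade 1 row, delete the figure and keep the unchanged-dose wording.
- In Appendix 10, print *20 or, if reduced, 10 mcg/kg/dose*.

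An explicit statement on whether re-escalation is ever allowed is optional and for the clinical leads to decide.

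The cost is three phrases in section 6.4 and one printed dose in Appendix 10, with no extra visits, data or patients.
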